14.1.2.4.4 New lesions

The appearance of a new lesion is always associated with Progressive Disease (PD) and has to be recorded as a new lesion in the New Lesion CRF page.

- If a new lesion is **equivocal**, for example because of its small size, continued therapy and follow-up evaluation will clarify if it represents truly new disease. If repeat scans confirm there is definitely a new lesion, then progression should be declared using the date of the first observation of the lesion

- If new disease is observed in a region which was **not scanned at baseline** or where the particular baseline scan is not available for some reason, then this should be considered as a PD. The one exception to this is when there are no baseline scans at all available for a patient in which case the response should be UNK, as for any of this patient's assessment (see [Section 14.1.2.5](#)).
- A **lymph node is considered as a “new lesion”** and, therefore, indicative of progressive disease if the short axis increases in size to ≥ 10 mm for the first time in the study plus 5 mm absolute increase.
FDG-PET: can complement CT scans in assessing progression (particularly possible for ‘new’ disease). See [Section 14.1.2.2](#).

14.1.2.5 Evaluation of overall lesion response

The evaluation of overall lesion response at each assessment is a composite of the target lesion response, non-target lesion response and presence of new lesions as shown below in Table 14-3.

Table 14-3 Overall lesion response at each assessment

Target lesions	Non-target lesions	New Lesions	Overall lesion response
CR	CR	No	CR ¹
CR	Non-CR/Non-PD ³	No	PR
CR, PR, SD	UNK	No	UNK
PR	Non-PD and not UNK	No	PR ¹
SD	Non-PD and not UNK	No	SD ^{1, 2}
UNK	Non-PD or UNK	No	UNK ¹
PD	Any	Yes or No	PD
Any	PD	Yes or No	PD
Any	Any	Yes	PD

1. This overall lesion response also applies when there are no non-target lesions identified at baseline.

2. Once confirmed PR was achieved, all these assessments are considered PR.

3. As defined in [Section 14.1.2.4](#).

[figure not shown]
If there are no baseline scans available at all, then the overall lesion response at each assessment should be considered Unknown (UNK).

If the evaluation of any of the target or non-target lesions identified at baseline could not be made during follow-up, the overall status must be ‘unknown’ unless progression was seen.

In some circumstances it may be difficult to distinguish residual disease from normal tissue. When the evaluation of complete response depends on this determination, it is recommended that the residual lesion be investigated (fine needle aspirate/biopsy) to confirm the CR.

14.1.3 Efficacy definitions

The following definitions primarily relate to patients who have measurable disease at baseline. [Section 14.1.3.2.8](#) outlines the special considerations that need to be given to patients with no measurable disease at baseline in order to apply the same concepts.

14.1.3.1 Best overall response

The best overall response is the best response recorded from the start of the treatment until disease progression/recurrence (taking as reference for PD the smallest measurements recorded since the treatment started). In general, the patient's best response assignment will depend on the achievement of both measurement and confirmation criteria.

The best overall response will usually be determined from response assessments undertaken while on treatment. However, if any assessments occur after treatment withdrawal the protocol should specifically describe if these will be included in the determination of best overall response and/or whether these additional assessments will be required for sensitivity or supportive analyses. As a default, any assessments taken more than 30 days after the last dose of study treatment will not be included in the best overall response derivation. If any alternative cancer therapy is taken while on study any subsequent assessments would ordinarily be excluded from the best overall response determination. If response assessments taken after withdrawal from study treatment and/or alternative therapy are to be included in the main endpoint determination, then this should be described and justified in the protocol.

Where a study requires confirmation of response (PR or CR), changes in tumor measurements must be confirmed by repeat assessments that should be performed not less than 4 weeks after the criteria for response are first met.

Longer intervals may also be appropriate. However, this must be clearly stated in the protocol. The main goal of confirmation of objective response is to avoid overestimating the response rate observed. In cases where confirmation of response is not feasible, it should be made clear when reporting the outcome of such studies that the responses are not confirmed.

- For non-randomized trials where response is the primary endpoint, confirmation is needed.
- For trials intended to support accelerated approval, confirmation is needed
- For all other trials, confirmation of response may be considered optional.

The best overall response for each patient is determined from the sequence of overall (lesion) responses according to the following rules:

- CR = at least two determinations of CR at least 4 weeks apart before progression where confirmation required or one determination of CR prior to progression where confirmation not required
- PR = at least two determinations of PR or better at least 4 weeks apart before progression (and not qualifying for a CR) where confirmation required or one determination of PR prior to progression where confirmation not required
- SD = at least one SD assessment (or better) > 6 weeks after randomization/start of treatment (and not qualifying for CR or PR).
- PD = progression ≤ 12 weeks after randomization/ start of treatment (and not qualifying for CR, PR or SD).
- UNK = all other cases (i.e. not qualifying for confirmed CR or PR and without SD after more than 6 weeks or early progression within the first 12 weeks)

Overall lesion responses of CR must stay the same until progression sets in, with the exception of a UNK status. A patient who had a CR cannot subsequently have a lower status

other than a PD, e.g. PR or SD, as this would imply a progression based on one or more lesions reappearing, in which case the status would become a PD.

Once an overall lesion response of PR is observed (which may have to be a confirmed PR depending on the study) this assignment must stay the same or improve over time until progression sets in, with the exception of an UNK status. However, in studies where confirmation of response is required, if a patient has a single PR ($\geq 30\%$ reduction of tumor burden compared to baseline) at one assessment, followed by a $< 30\%$ reduction from baseline at the next assessment (but not $\geq 20\%$ increase from previous smallest sum), the objective status at that assessment should be SD. Once a confirmed PR was seen, the overall lesion response should be considered PR (or UNK) until progression is documented or the lesions totally disappear in which case a CR assignment is applicable. In studies where confirmation of response is not required after a single PR the overall lesion response should still be considered PR (or UNK) until progression is documented or the lesion totally disappears in which case a CR assignment is applicable.

Example: In a case where confirmation of response is required the sum of lesion diameters is 200 mm at baseline and then 140 mm - 150 mm - 140 mm - 160 mm - 160 mm at the subsequent visits. Assuming that non-target lesions did not progress, the overall lesion response would be PR - SD - PR - PR - PR. The second assessment with 140 mm confirms the PR for this patient. All subsequent assessments are considered PR even if tumor measurements decrease only by 20% compared to baseline (200 mm to 160 mm) at the following assessments.

If the patient progressed but continues study treatment, further assessments are not considered for the determination of best overall response.

Note: these cases may be described as a separate finding in the CSR but not included in the overall response or disease control rates.

The best overall response for a patient is always calculated, based on the sequence of overall lesion responses. However, the overall lesion response at a given assessment may be provided from different sources:

- Investigator overall lesion response
- Central Blinded Review overall lesion response
- Novartis calculated overall lesion response (based on measurements from either Investigator or Central Review)

The primary analysis of the best overall response will be based on the sequence of investigator overall lesion responses.

Based on the patients' best overall response during the study, the following rates are then calculated:

Overall response rate (ORR) is the proportion of patients with a best overall response of CR or PR. This is also referred to as 'Objective response rate' in some protocols or publications.

Disease control rate (DCR) is the proportion of patients with a best overall response of CR or PR or SD.

Another approach is to summarize the progression rate at a certain time point after baseline. In this case, the following definition is used:

Early progression rate (EPR) is the proportion of patients with progressive disease within 8 weeks of the start of treatment.

The protocol should define populations for which these will be calculated. The timepoint for EPR is study specific. EPR is used for the multinomial designs of Dent and Zee (2001) and counts all patients who at the specified assessment (in this example the assessment would be at 8 weeks \pm window) do not have an overall lesion response of SD, PR or CR. Patients with an unknown (UNK) assessment at that time point and no PD before, will not be counted as early progressors in the analysis but may be included in the denominator of the EPR rate, depending on the analysis population used. Similarly when examining overall response and disease control, patients with a best overall response assessment of unknown (UNK) will not be regarded as “responders” but may be included in the denominator for ORR and DCR calculation depending on the analysis population (e.g. populations based on an ITT approach).

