3.9 Assessment windows, baseline and post-baseline definitions, missing data handling

3.9.1 Assessment windows

Patients will be assessed at baseline (day -28 to -1) and will then attend up to 16 visits during the core study with a separate assessment being completed at the end of the core study (EOCS) (12 months), either completion or early withdrawal. Those patients presenting with clinical benefit and not experiencing unacceptable toxicity at the 12 month visit will continue into the extension phase until progression occurs. They will attend visits every 3 months with a separate assessment being completed at the end of the extension phase (EOEP) when progression occurs, patient withdraws or two years after treatment start of the last evaluable patient. All patients who discontinue study treatment must have safety evaluations 56 days after the last dose of pasireotide LAR or everolimus, whichever comes last. This includes those who didn't enter extension phase due to disease progression at week 52. Endpoints (i.e. EOCS and EOEP) will be summarized as per scheduled visits. Any data from unscheduled

visits (Unsch), will be listed. Early withdrawal visits will continue to be displayed at the EOCS visit i.e. it will not be re-mapped to the most appropriate visit.

Visits will be labeled as follows: Baseline, Day 1, Day 15, Day 21, Day 29, Day 49, Day 57, Day 85, Day 113, Day 141, Day 169, Day 197, Day 225, Day 253, Day 281, Day 309, Day 337, EOCS, 3 Mths Extn, 6 Mths Extn, 9 Mths Extn, 12 Mths Extn, 15 Mths Extn, ..., EOEP, Safety FU, Unsch.

The tumor assessments will be time-slotted using the time windows displayed in Table 2.

Table 2 - Time windows for tumor assessments

Time Window	Planned Visit Timing	Time Window Definition
Week 12	Study Day 85 (Week 12)]0; 126] days or]0; 18] weeks
Week 24	Study Day 169 (Week 24)]126; 210] days or]18; 30] weeks
Week 36	Study Day 253 (Week 36)]210; 294] days or]30; 42] weeks
Week 48	Study Day 337 (Week 48)]294; 351] days or]42; 50] weeks
Week 52	Study Day 365 (Week 52)]351; 379] days or]50; 54] weeks
Week 64	Study Day 449 (Week 64)]379; 491] days or]54; 70] weeks
Week k	Study Day x (Week y) x= k*7+1 ; y=k]x-43; x+41] days or]y-6; y+6] weeks

Study Day 1 = start of study treatment date

Similarly to tumor assessments, week-based time windows [REDACTED]. If more non-missing results fall into a specific time window, then the one will be chosen which is closer to the optimal study day of the specific time window.

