6.1 Implementation of RECIST

Tumor response and disease progression will be evaluated according to the Novartis guidelines based on RECIST 1.1 criteria (enclosed in protocol Appendix 1), unless otherwise noted.

The evaluation of overall lesion response at each assessment is a composite of the target lesion response, non-target lesion response and presence of new lesions as shown below. This information will be captured on the CRF.

Table 4 - Evaluation of overall lesion response

Target lesions	Non-target lesions	New Lesions	Overall lesion response
CR	CR	No	CR ¹
CR	Non-CR/Non PD	No	PR
CR, PR, SD	UNK	No	UNK
PR	Non-PD and not UNK	No	PR ¹
SD	Non-PD and not UNK	No	SD ^{1,2}
UNK	Non-PD or UNK	No	UNK ¹
PD	Any	Yes or No	PD
Any	PD	Yes or No	PD
Any	Any	Yes	PD

¹ This overall lesion response also applies when there are no non target lesions identified at baseline.
² Once confirmed PR was achieved, all these assessment are considered PR.

A listing of the tumor assessments and responses will be presented for the full analysis set after completion of core phase and extension phase analyses. This will include evaluation number, type of lesion (target, non-target, new), overall assessment, number, location, measurement method, evaluation date, longest diameter (cm), lesion status and an overall lesion response as per the investigator. Patients who discontinue study treatment after 12 months of treatment without evidence of progression or for reasons other than disease progression will continue to have tumor evaluation assessments unless consent is withdrawn. These will be flagged in this listing.

Another listing of lesion locations and descriptions will also be produced for the full analysis set. This will include the evaluation number, the type of lesion (target, non-target, new), the

number, the evaluation date, the location, the description, the measurement method and the measurement method detail.

For each time to event assessment, the assessment date is calculated as follows:

- the latest of all measurement dates for assessment with overall lesion response = CR, PR, SD or UNK.
- the earliest of all measurement dates for assessments with overall lesion response = PD.

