7.5 Objective Response Rate

The objective response rate is defined as the proportion of patients showing a best overall response of CR or PR during the core study (i.e. up to 12 months) according to RECIST V. 1.1 criteria. For the assessment of SD as best overall response, there is no specific time needed from baseline as the first tumor evaluation takes place after 12 weeks (at Visit 8) from randomization thus conforming the required minimum time of 6 weeks from randomization based on RECIST 1.1 guidelines. Therefore, the best overall response is interpreted as the best response recorded from the start of the treatment until disease progression/recurrence, death from any cause or until the patient withdraws consent, whichever is earliest. In order to have a best overall response of CR or PR, response must be confirmed by another response assessed at least 4 weeks after the initial response. The objective response rate will be calculated at 12 months and displayed with 95 percent exact binomial confidence intervals (implemented using SAS procedure FREQ with EXACT statement for one-way tables) [Clopper & Pearson, 1934]. Frequencies of each response will also be included. This will be carried out for all patients in the full analysis set.

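### The 12-week limit for a best overall response of PD falls on the planned first scan day, so documented progression at that scan can be tabulated as unknown

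*Protocol*

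**What the plan says.** Protocol Appendix 14.1.3.1 derives BOR from the sequence of overall lesion responses. PD requires progression at or before "12 weeks after randomization/ start of treatment (and not qualifying for CR, PR or SD"). The residual category is "UNK = all other cases (i.e. not qualifying for confirmed CR or PR and without SD after more than 6 weeks", and it also takes any progression that misses the 12-week limit.

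SAP 6.1 evaluates response and progression "according to the Novartis guidelines based on RECIST 1.1 criteria (enclosed in protocol Appendix 1), unless otherwise noted".

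SAP Table 2 (section 3.9.1) plans the first on-treatment tumor assessment for "Study Day 85 (Week 12"), with "Study Day 1 = start of study treatment date". Its Week 12 window accepts assessments up to Day 126.

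SAP 7.5 says of SD that "there is no specific time needed from baseline as the first tumor evaluation takes place after 12 weeks (at Visit 8) from randomization". It then restates BOR in general terms, as the best response seen before progression, death or withdrawal of consent. It gives no rule of its own for PD or UNK. On output it says: "Frequencies of each response will also be included".

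**The concern.** The PD limit and the first scan share a boundary. A patient whose first scan shows progression has no earlier SD to fall back on. If that scan is dated after the limit, the appendix leaves only UNK, although the progression is documented. SAP 7.5 itself places the first evaluation after 12 weeks. It uses that timing to dispense with a minimum time for SD but is silent on the PD limit.

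BOR is a named secondary endpoint, and the frequency of each category is to be reported. Read literally, the rule would show some early progressors as unevaluable. That would understate early progression and overstate unknown outcomes in that table. The split would also depend on scan logistics and an unstated day count, not on the disease.

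**Working it through.** **Inputs**

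- PD limit: 12 weeks = 84 days, counted from randomization or start of treatment; the appendix leaves both open (Protocol 14.1.3.1).
- UNK includes a patient "without SD after more than 6 weeks or early progression within the first 12 weeks" (same section).
- Planned assessment day: x = 7k + 1 for week k, with Study Day 1 at treatment start (SAP Table 2).
- Day count: end − start + 1 for time-to-event variables (Protocol 14.1.4.5.1). No count is stated for the BOR limit.
- Scan interval: every 3 months, or at the end-of-study visit if earlier, with no tolerance given (Protocol 7.2.1.1.1). The ±7-day tolerance is stated under safety assessments (Protocol 7.2.2).

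**Step 1. Reproduce the planned day.** For k = 12, x = 7 × 12 + 1 = 85, as in Table 2.

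**Step 2. Place Day 85 against the limit.**

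- Elapsed days: 85 − 1 = 84, and 84/7 = 12.00 weeks. Day 85 is inside the limit; Day 86 is the first day outside.
- With the +1 count: 85 days, and 85/7 = 12.14 weeks. Day 85 is already outside.

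**Step 3. Share of first-scan progressors turned into UNK.** The documents give no distribution of scan dates, so each row below is an assumption. Share = scan days beyond the limit divided by all scan days in the spread.

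| Assumed first-scan days | Elapsed count | +1 count |
|---|---|---|
| All on Day 85 | 0% | 100% |
| Even, Days 82–88 (±3) | 3/7 = 42.9% | 4/7 = 57.1% |
| Even, Days 78–92 (±7) | 7/15 = 46.7% | 8/15 = 53.3% |
| Days 78–92, triangular weights peaking at Day 85 | 28/64 = 43.8% | 36/64 = 56.2% |
| Even ±7, centred 3 days early (75–89) | 4/15 = 26.7% | 5/15 = 33.3% |
| Even ±7, centred 3 days late (81–95) | 10/15 = 66.7% | 11/15 = 73.3% |
| Even ±7, centred on Day 92, about 3 calendar months (85–99) | 14/15 = 93.3% | 15/15 = 100% |

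Counting from randomization with an assumed 3-day lag to Day 1 has the same effect as the 3-day late row: 66.7% to 73.3%.

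**Step 4. Which results use the rule.**

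- ORR and DCR: PD and UNK are both non-successes (Protocol 14.1.3.1), and both stay in the full analysis set denominator. No change.
- Month 9 endpoint: uses the overall lesion response at Month 9, with the Week 48 and Week 52 fallback (SAP 6.3.1). It does not use BOR.
- PFS: uses the progression date (SAP 7.1). It does not use BOR.
- BOR frequencies (SAP 7.5): the PD and UNK rows change.

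**Step 5. Effect of moving the limit to Study Day 126.** No patient with documented progression on or before Day 126 would become UNK. The ambiguities of day count and anchor also disappear, because a Study Day is already defined from treatment start.

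**The case against.** The best counter-argument is that SAP 7.5 does note otherwise. It interprets BOR as the best response recorded up to progression, death or consent withdrawal, and Protocol 3.2 and 10.5.2 also define BOR without a 12-week limit. On that reading, a patient whose only assessment is PD has a BOR of PD. The reading is possible but not secure. Appendix 14.1.3.1 opens with nearly the same general definition and then applies the 12-week limit beneath it, so restating the definition does not clearly remove the limit. A programmer would have to choose.

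Second, a reader might infer that about half of first-scan progressors are classified as unknown. The documents do not support that as a finding. It needs scan dates symmetric around Day 85, and the ±7-day tolerance belongs to the safety assessments. That list does include the gallbladder assessment, which Protocol 7.2.2.6.4 schedules with the tumor scan in patients on pasireotide LAR. This gives the tolerance some indirect support in two arms, but none for everolimus alone. In addition, patients leaving early are scanned at their end-of-study visit, and a PD assessment takes its earliest measurement date (SAP 6.1). Both pull progression dates earlier, towards PD. This part of the objection stands.

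Third, the consequence is small. Early progression also shows in the 3-month Kaplan-Meier PFS estimate, the reasons for discontinuation and the response listings. This also stands, and it limits the point to one descriptive table.

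**Conclusion.** The point holds as an unresolved conflict between the appendix rule and the scan schedule. Followed literally, the plan can report documented progression at the first scan as UNK, and SAP 7.5 does not expressly prevent it.

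The share cannot be derived from the documents. The figure of 47% to 53% illustrates one assumption, an even ±7-day spread around Day 85; the full range is 0% to 100%. The number of first-scan progressors to which any such share applies is not given either.

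A reader might also infer that response or disease control rates are distorted. They are not, and neither are the Month 9 decision or PFS. The matter is minor, but worth settling because BOR is a named secondary endpoint.

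**What to change.** In SAP 7.5, replace the 12-week limit with this rule: BOR is PD when progression is documented on or before Study Day 126 (the end of the Week 12 window in Table 2, counted from start of treatment) and the patient does not qualify for CR, PR or SD.

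The rule should not require the progression to be at the first post-baseline assessment. A patient with an early scan read as UNK and documented progression by Day 84 is PD under the present limit and should stay PD.

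Progression first documented after Day 126 with no earlier qualifying assessment would remain UNK, as now.

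The cost is one SAP sentence, one programming limit and possibly one table. ORR and its response frequencies are core-phase results. Protocol Amendment 5 dates the primary analysis to February 2016, and SAP 3.4.2 does not list BOR among the analyses repeated after the extension. If the core-phase BOR table was produced under the literal limit, it must be recounted or footnoted.
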